3.0 STUDY DESIGN

- This will be a phase I/II, two-arm, open-label study.
- Patients will receive therapy with quizartinib orally daily on 28 day cycles.
- In addition patients will receive either AZA subcutaneously or intravenously daily for the first 7 days of each treatment cycle or LDAC subcutaneously twice daily for the first 10 days of each treatment cycle. Cycles will be repeated approximately every 28 days, and therapy will be continued until clinically significant disease progression or documentation of unacceptable toxicity.

4.0 PATIENT SELECTION

Patients must have baseline evaluations performed prior to the first dose of study drug and must meet all inclusion and exclusion criteria. Results of all baseline evaluations, which assure that all inclusion and exclusion criteria have been satisfied, must be reviewed by the Principal Investigator or his/her designee prior to enrollment of that patient. In addition, the patient must be thoroughly informed about all aspects of the study, including the study visit schedule and required evaluations and all regulatory requirements for informed consent. The written informed consent must be obtained from the patient prior to initiating treatment. The following criteria apply to all patients enrolled onto the study unless otherwise specified.

4.1 Inclusion Criteria

4.1.1 Patients with MDS, CMML or AML

4.1.2 For Phase I only

4.1.2.1 Refractory or relapsed disease defined as follows:

4.1.2.1.1 Patients with MDS or CMML should have failed prior therapy (e.g., with a hypomethylating agent, clofarabine, and/or with lenalidomide).

4.1.2.1.2 Patients with AML should have failed any prior induction therapy or have relapsed after prior therapy.

4.1.2.1.3 Patients (any age) with MDS or CMML who received therapy with a hypomethylating agent and progress to AML are eligible at the time of diagnosis of AML regardless any prior therapy for AML. The WHO classification will be used for AML.

4.1.2.1.4 Patients with any of the eligible diagnoses who have received no prior therapy are eligible if not candidates to receive standard intensive therapy (ie, high-dose cytarabine-based chemotherapy).

4.1.2.2 Patients are eligible regardless of their FLT3 mutation status

4.1.2.3 Age \geq 18 years

4.1.3 For Phase II only: two cohorts will be enrolled:

4.1.3.1 Cohort 2A – FLT3-ITD:

4.1.3.1.1 Patients with MDS, CMML or AML who are either:

4.1.3.1.1.1 Age 60 years or older and newly diagnosed, previously untreated. Prior therapy with hydroxyurea or single agent ara-C for the purpose of control of WBC is acceptable.

4.1.3.1.1.2 Age 18 years or older and with refractory or relapse disease who have received no more than

one prior treatment regimen and will be receiving first salvage. For this purposes, a second induction cycle with the same drugs used during the first cycle, consolidation chemotherapy or stem cell transplant in CR (or CRp or CRi) will be considered part of the prior regimen. Prior therapy for MDS (or other malignancies) is not considered a prior regimen for AML in patients who progress from MDS (or other malignancies).

4.1.3.1.2 Patients (any age) with MDS or CMML who received therapy with a hypomethylating agent and progress to AML are eligible regardless of any prior therapy for AML. The WHO classification will be used for AML.

4.1.3.1.3 Patients must have evidence of FLT3 ITD in their most recent assessment.

4.1.3.2 Cohort 2B – FLT3-WT:

4.1.3.2.1 Patients with MDS, CMML or AML who are either:

4.1.3.2.1.1 Age 60 years or older and newly diagnosed, previously untreated. Prior therapy with hydroxyurea or single agent ara-C for the purpose of control of WBC is acceptable.

4.1.3.2.1.2 Age 18 years or older and with refractory or relapse disease who have received no more than two prior treatment regimens and will be receiving second salvage, or who have received a prior SCT and will be receiving their first salvage. For this purposes, a second induction cycle with the same drugs used during the first cycle, consolidation chemotherapy or stem cell transplant in CR (or CRp or CRi) will be considered part of the prior regimen. Prior therapy for MDS (or other malignancies) is not considered a prior regimen for AML in patients who progress from MDS (or other malignancies).

4.1.3.2.2 Patients (any age) with MDS or CMML who received therapy with a hypomethylating agent and progress to AML are eligible at the time of diagnosis of AML regardless any prior therapy for AML. The WHO

classification will be used for AML.

4.1.3.2.3 Patients must have no evidence of FLT3 mutations in their most recent assessment.

4.1.4 For Phase I and II

4.1.4.1 ECOG Performance Status ≤ 2

4.1.4.2 Adequate liver (bilirubin $\leq 2x$ ULN, ALT $\leq 2.5x$ ULN) and renal (creatinine $\leq 2x$ ULN) function. For patients with suspected liver infiltration from leukemia, ALT should be $\leq 5x$ ULN.

4.1.4.3 Serum potassium, magnesium, and calcium (normalized for albumin) levels should be at least within institutional normal limits.

4.1.4.4 Patients must provide written informed consent.

4.1.4.5 Patients must have been off chemotherapy for 2 weeks prior to entering this study, unless there is evidence of rapidly progressive disease, and must have recovered from the toxic effects of that therapy to at least grade 1. Use of hydroxyurea for patients with rapidly proliferative disease is allowed before the start of study therapy and for the first four weeks on therapy. The additional days of Hydrea after 28 is permitted as clinically indicated, on case by case basis and after discussion with the PI. Other agents given transiently with the intention to control rapid proliferation such as 1-2 doses of single agent ara-C or few doses of sorafenib are also allowed.

4.1.4.6 Women of childbearing potential must practice contraception. Women considered not of childbearing potential include any of the following: no menses for at least 2 years or menses within 2 years but amenorrheic for at least 2 months and luteinizing hormone (LH) and follicular stimulating hormone (FSH) values within normal range (according to definition of postmenopausal for laboratory used) or bilateral oophorectomy or radiation castration and amenorrheic for at least 3 months. Females of childbearing potential should practice effective methods of contraception. Effective methods of contraception include barrier methods (e.g., condoms, diaphragm), spermicidal jelly or foam, oral, depo provera, or injectable contraceptives, intrauterine devices, tubal ligation, and abstinence. Male patients with female partners who are of childbearing potential should also practice contraception.

4.1.5 Negative urine or serum pregnancy test.

4.2 Exclusion Criteria

- 4.2.1 Patients with known allergy or hypersensitivity to quizartinib, mannitol, AZA, cytarabine or any of their components.
- 4.2.2 Patients with electrolyte abnormalities at study entry defined as follows:
 - 4.2.2.1 Serum potassium < 3.5 mEq/L despite supplementation, or > 5.5 mEq/L.
 - 4.2.2.2 Serum magnesium above or below the institutional normal limit despite adequate management.
 - 4.2.2.3 Serum calcium (corrected for albumin levels) above or below institutional normal limit despite adequate management.
- 4.2.3 Patients with known significant impairment of gastrointestinal (GI) function or GI disease that may significantly alter the absorption of quizartinib.
- 4.2.4 Patients with any other known disease concurrent severe and/or uncontrolled medical condition (e.g. uncontrolled diabetes, cardiovascular disease including congestive heart failure, myocardial infarction within 6 months and poorly controlled hypertension, chronic renal disease, or active uncontrolled infection) which could compromise participation in the study. Patients with current active malignancies or any remission for < 6 months, except patients with carcinoma in situ or with non-melanoma skin cancer who may have active disease or be in remission for less than 6 months.
- 4.2.5 Patients with a known confirmed diagnosis of HIV infection or active viral hepatitis.
- 4.2.6 Patients who have had any major surgical procedure within 14 days of Day 1.
- 4.2.7 Patients with known malignant disease of the central nervous system.
- 4.2.8 Impaired cardiac function including any of the following
 - 4.2.8.1 Screening ECG with a QTc > 450 msec. The QTc interval will be calculated by Fridericia's correction factor (QTcF) at Screening and on Day 5 prior to the first dose of AC220. The QTcF will be derived from the average QTcF in triplicate. If QTcF > 450 msec on Day 5, AC220 will not be given.
 - 4.2.8.2 Patients with congenital long QT syndrome

- 4.2.8.3 History or presence of sustained ventricular tachycardia requiring medical intervention
 - 4.2.8.4 Any history of clinically significant ventricular fibrillation or torsades de pointes
 - 4.2.8.5 Known history of second or third degree heart block (may be eligible if the patient currently has a pacemaker)
 - 4.2.8.6 Sustained heart rate of <50/minute on pre-entry ECG
 - 4.2.8.7 Right bundle branch block + left anterior hemiblock (bifascicular block)
 - 4.2.8.8 Patients with myocardial infarction or unstable angina within 6 months prior to starting study drug
 - 4.2.8.9 CHF NY Heart Association class III or IV
 - 4.2.8.10 Atrial fibrillation documented within 2 weeks prior to first dose of study drug.
 - 4.2.8.11 Patients who require treatment with concomitant drugs that prolong QT/QTc interval or strong CYP3A4 inhibitors or inducers with the exception of antibiotics, antifungals, and antivirals that are used as standard of care to prevent or treat infections and other such drugs that are considered absolutely essential for the care of the subject.
- 4.2.9 Known family history of congenital long QT syndrome

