5.2 Schedule

5.2.1 Patients will be treated according to the following schedule:

- AZA will be administered subcutaneously (SQ) or intravenously (IV) for 7 days of every cycle (Days 1-7) as determined by the treating physician. Both SQ and IV forms of administration are FDA approved and considered interchangeable. Patients may start receiving AZA IV and changed to SQ at any time (and vice versa) as needed based on patient and physician preference. AZA is administered in the clinic or chemotherapy administration area.
- Cytarabine will be administered SQ twice daily for 10 days of every cycle (Days 1-10) as determined by the treating physician. Cytarabine can be self-administered by the patient.
- Quizartinib will be administered orally daily for 28 days of every cycle. For the first cycle only, quizartinib will be administered starting on day 5 of the cycle. All subsequent cycles quizartinib will start concomitantly with AZA or cytarabine.

5.2.1.1 The starting and target dose is dose level 1.

Table 1(a): Dose reduction and escalation for Cytarabine + AC220 treatment arm

Dose Level	Cytarabine (mg BID x 10 days)	AC220 (mg/d, uninterrupted)
-3	10	30
-2	15	30
-1	20	30
1 (Starting and target dose)	20	60
2	20	90

Table 1(b): Dose reduction and escalation for AZA+ AC220 treatment arm

Dose Level	AZA (mg/m ² /d x 7 days)	AC220 (mg/d, uninterrupted)
-3	25	30
-2	50	30
-1	75	30
1 (Starting and target dose)	75	60
2	75	90

- 5.2.1.2** Dose reductions beyond those mentioned in this table or different to the doses specified should be discussed with the PI and documentation of the justification recorded in the chart.
- 5.2.2** Patients will be assigned to treatment arm by physician's choice and according to the availability of slots.
- 5.2.2.1** Treatment arm is defined by the use of each of the possible chemotherapy agents (i.e., AZA + AC220 is one treatment arm and Cytarabine + AC220 is another treatment arm).
- 5.2.2.2** Patients in Cohort 2B (FLT3 WT) will only be treated with AZA + AC220. The combination with cytarabine will not be explored in this subset of patients in this study.
- 5.2.3** The first 6 patients on each cohort will receive dose level 1. At least 3 of the patients will be females.
- 5.2.3.1** A cohort is defined by each dose level.
- 5.2.4** Prior to advancing/changing cohorts a cohort summary will be completed and submitted to the Medical Monitor in the IND Office.

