- 5.2.5** DLT is defined as any clinically significant non-hematologic adverse event or abnormal laboratory value occurring during the first cycle on study unless the event or laboratory value can clearly be determined to be unrelated to AC220 with the following exceptions:
- CTCAE Grade 3 or 4 AST (SGOT) or ALT (SGPT) that resolves to \leq grade 2 in 14 days
 - Grade 3 nausea, vomiting, or diarrhea that can be managed to \leq grade 2 with standard antiemetic or antidiarrheal medications used at prescribed dose within 7 days of onset.
 - Grade 4 vomiting, or diarrhea that can be managed to \leq grade 3 with standard antiemetic or antidiarrheal medications used at prescribed dose within 48 hours of onset.
 - Grade 3 or 4 electrolyte abnormalities will only be considered DLT if possibly related to study drug and not corrected by optimal replacement therapy within 48 hours.
 - Grade 3 biochemical abnormalities of amylase or lipase without evidence of clinical pancreatitis.
 - Grade 3 anorexia or fatigue.
 - Grade 3 or 4 QTc prolongation will constitute DLT as follows: The QTc interval will be calculated by Fridericia's correction factor (QTcF). If the QTc is > 500 msec the EKG must be evaluated within 2 hours in triplicate and if \geq grade 3 QTc prolongation is confirmed this will be considered a DLT.

Hematologic DLT is defined as grade ≥ 3 neutropenia and/or thrombocytopenia with a hypocellular bone marrow lasting for 6 weeks or more after the start of a course in the absence of residual leukemia (i.e., with less than 5% blasts). Anemia will not be considered for the definition of DLT.

- 5.2.5.1** If DLT occurs in $\geq 2/6$ patients, this dose level would exceed the MTD, and an additional 6 patients will be treated at the next lower dose level. The dose level at which 0-1/6 patients experience DLT (but not higher than 60 mg/day) will be used to treat a maximum of 20 patients in each cohort in the phase II portion of the study. If $\geq 2/6$ patients experience DLT at dose level -1 in any arm, dose level -2 may be explored for that arm(s).
- 5.2.5.2** If DLT is observed in 0 or 1/6 in dose level 1, this cohort will be expanded to treat up to 20 patients in the phase II portion of the study. If $\geq 2/6$ patients experience DLT at dose level 1 for any arm of the study, the dose level at which $\leq 1/6$ patients have experienced DLT will be used for the phase II portion of the study for that arm.

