- 5.2.5.3** If DLT is observed in 2/6 patients treated at dose level 1 in any arm, the study will continue at the quizartinib dose of 30 mg PO (dose level -1) for that arm to treat an additional 26 patients at this dose level in the phase II portion of the study.
- 5.2.5.4** Patients that are removed from study before day 28 for any reason other than toxicity and have not experienced DLT will be replaced.
- 5.2.5.5** DLT and MTD will be defined independently for each treatment arm (i.e., AC220 + AZA and AC220 + cytarabine).
- 5.2.6** One cycle of therapy is defined 7 days of AZA or 10 days of LDAC, and 28 days of quizartinib. Patients will receive one cycle of therapy every 4 weeks.
 - 5.2.6.1** Cycles may be started early (but not earlier than day 21) for patients with active disease if judged in the best interest of the patient.
 - 5.2.6.2** Subsequent cycles may be delayed for recovery of toxicity. Delays in start of subsequent cycles greater than 8 weeks should be discussed with the principal investigator.

5.2.6.3 Quizartinib therapy may continue if there is a delay in the start of the next cycle of AZA provided the delay is not due to toxicity possibly related to quizartinib.

5.2.6.4 Subsequent courses may be administered regardless of peripheral blood counts during the first 4 cycles and/or in the presence of residual leukemia. If prolonged myelosuppression (more than 60 days) with evidence of a hypocellular marrow (marrow cellularity less than 5% without evidence of leukemia) is observed subsequent courses of AZA may be given at the next lower dose. If the peripheral counts do not recover (ANC $<1 \times 10^9/L$ and/or platelets $<30 \times 10^9/L$) but there is evidence of residual leukemia in the bone marrow, subsequent cycles can be administered at the discretion of the treating physician not earlier than 3 weeks after the prior cycle.

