5.3 Duration of Therapy

In the absence of treatment delays due to adverse events, treatment may continue until one of the following criteria applies:

1. Clinically significant progressive disease
2. Grade 4 QTc prolongation.
3. Intercurrent illness that prevents further administration of treatment

4. Patient request
5. General or specific changes in the patient's condition render the patient unacceptable for further treatment in the judgment of the investigator.
6. Unacceptable toxicity that in the opinion of the investigator makes it unsafe to continue therapy. This includes patients with grade 4 non-hematological toxicity unless it reverses to grade ≤ 1 on or before 14 days of interrupting AC220.

5.3.1 It is planned that up to a total of 12 cycles of therapy will be administered for patients deriving benefit from this regimen. Continuation of therapy for patients completing 12 cycles of therapy may be considered on a case by case basis after discussion with the principal investigator.

5.3.2 A minimum of 1 full course (defined as the administration of AZA for 7 days or LDAC for 10 days, and quizartinib for 24 days for cycle one, i.e. days 5-28) will be required for a patient to be considered as having received an adequate trial to evaluate efficacy. All patients receiving at least one dose of any of the two drugs will be considered evaluable for toxicity.

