12.2 Phase I

The primary objective of the phase I portion of the study is to determine the MTD of each combination therapy. The dose schedule is listed in table 1 of section 5.2.1. Up to 2 dose levels of AC220 will be tested in each combination with a fixed dose of the other drug. Initially, 6 patients will be treated at dose level1, if ≤ 1 patients experience DLT at dose level1, then 6 subsequent patients will be treated at the next higher dose level, dose level2. If ≤ 1 patients experience DLTs in dose level2, this level will be defined as the MTD and will be used in the phase II portion of the study. If > 1 patients experience DLTs at dose level1, then the 6 subsequent patients will be treated at the next lower dose level, level -1. The MTD is defined as the highest dose at which no more than 1 patient experiences DLTs. For each combination therapy, 12 patients will be evaluated. The total sample size for the phase I portion will be 24.

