12.3 Phase II

A: Cohort 2A – FLT3-ITD

The primary endpoint of the phase II portion of the study is overall response (CR+Cri+PR+HI) (first 2 treatment courses). It would be encouraging if the overall response rate reaches 50%.

Treatment with AC220 + low-dose cytarabine (Cohort 2A-FLT3-ITD)

Patients enrolled in the treatment of AC220 + low-dose cytarabine could be newly diagnosed or previously treated. A total of 26 patients (including 6 patients treated at MTD in Phase I) will be treated with this treatment combination. The toxicity and efficacy (CR+Cri+PR+HI) will be monitored during the study, and all the data will be used to update the prior distributions for toxicity and efficacy parameters. The study will be stopped for toxicity and futility based on the following stopping rules. If the trial for this treatment continues until 26 patients are evaluated, and assuming the overall response rate is 50%, then the 95% credible interval for overall response rate would be (0.32, 0.68).

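### The DLT counts require no AC220 exposure, so a patient who receives only AZA or LDAC can hold an unreplaced DLT slot

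*Combined protocol and SAP*

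**What the plan says.** - **Timing (5.2.1).** AZA or LDAC begins on Day 1. For AC220: "For the first cycle only, quizartinib will be administered starting on day 5 of the cycle".
- **Day 5 check (4.2.8.1).** "If QTcF > 450 msec on Day 5, AC220 will not be given". The sentence sits within an exclusion criterion. It does not say whether the patient leaves the study, continues the other drug alone, is re-tested, or counts as a toxicity removal. The stopping reasons in 5.3 do not name a failed Day 5 check; their only QTc item is Grade 4 prolongation.
- **Toxicity set (5.3.2).** "All patients receiving at least one dose of any of the two drugs will be considered evaluable for toxicity". The same paragraph requires quizartinib on days 5-28 of cycle 1 for a patient to count as an adequate efficacy trial.
- **Replacement (5.2.5.4).** "Patients that are removed from study before day 28 for any reason other than toxicity and have not experienced DLT will be replaced".
- **DLT attribution (5.2.5).** A non-hematologic event in the first cycle counts "unless the event or laboratory value can clearly be determined to be unrelated to AC220". The hematologic DLT definition has no such attribution clause.
- **Decision rules.** In 5.2.5.2: "If DLT is observed in 0 or 1/6 in dose level 1, this cohort will be expanded". In 12.2: "The MTD is defined as the highest dose at which no more than 1 patient experiences DLTs". In 12.3, phase II toxicity is defined as DLTs and stopping is by DLT counts over numbers of patients, with no evaluable set defined.
- **Carry-over (12.3).** For LDAC: "A total of 26 patients (including 6 patients treated at MTD in Phase I". The AZA groups likewise include phase I patients treated at the same dose.

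**The concern.** The phase I decision and the phase II toxicity rule are both meant to measure the DLT rate of a combination that contains AC220. A patient who never takes AC220 carries almost no information about that rate, yet nothing in the plan keeps such a patient out of the denominator. Two routes remain open after 5.2.5.4 is applied:

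1. AC220 is withheld on Day 5 and the patient stays on AZA or LDAC alone through day 28. The patient has not been removed, so is not replaced.
2. The patient is removed before any AC220 because of a toxicity that is not a DLT, such as a Day 1-4 event clearly unrelated to AC220. The removal is for toxicity, so the patient is not replaced.

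Either patient can stand as one of the six with no DLT. This makes a too-toxic dose more likely to pass, and the same patient can carry over into the phase II count. The Day 5 check also selects on QTcF, and section 2.4 names QTc prolongation as the dose-limiting toxicity of quizartinib. The patients left unexposed by that check may therefore not be typical in QTc risk.

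**Working it through.** **Inputs from the plan.** Phase I: six patients per dose level, with at least two DLTs exceeding the MTD (5.2.5.1, 12.2). Phase II AZA groups (12.3): prior beta(0.6, 1.4) on the toxicity rate; stop if the posterior probability of a rate above 0.30 exceeds 0.9; looks at 15, 20, ..., 45 patients; maximum 50.

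**Inputs assumed.** The documents give neither the number of patients without AC220 nor the true DLT rate. I take 0, 1 or 2 unexposed among six, and 0%, 5%, 10% or 20% in phase II. Unexposed patients are given a DLT probability of zero, which makes the dilution as large as it can be for a given fraction.

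**Step 1: reproduce the plan's figures.** The boundary at n patients is the smallest x for which 1 − BetaCDF(0.30; 0.6 + x, 1.4 + n − x) > 0.90. At n = 15, x = 7 gives 0.893 (continue) and x = 8 gives 0.960 (stop). Across all looks the result is 8/15, 9/20, 11/25, 13/30, 15/35, 16/40 and 18/45, as stated in 12.3. Exact recursion with both stopping rules at response 0.5 and toxicity 0.3 gives an early-stopping probability of 0.247 and an average of 43.67 patients. Table 2 gives 0.247 and 43.7.

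**Step 2: phase I.** With m exposed patients in the six slots and true DLT rate p,

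P(at least 2 DLTs) = 1 − (1 − p)^m − m·p·(1 − p)^(m−1).

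At p = 0.33:
- m = 6: 1 − 0.0905 − 0.2673 = 0.642
- m = 5: 1 − 0.1350 − 0.2228·(0.3325/0.2228) = 1 − 0.1350 − 0.3325 = 0.532
- m = 4: 1 − 0.2015 − 0.3970 = 0.401

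| True DLT rate | 6 exposed | 5 exposed | 4 exposed |
|---|---|---|---|
| 0.30 | 0.580 | 0.472 | 0.348 |
| 0.33 | 0.642 | 0.532 | 0.401 |
| 0.40 | 0.767 | 0.663 | 0.525 |

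The complement is the chance that the dose passes. At 0.30 it rises from 0.420 to 0.528 and then 0.652.

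**Step 3: phase II.** If a fraction q of counted patients is unexposed, the counted DLT rate is p(1 − q). At p = 0.40 this is 0.38, 0.36 and 0.32 for q = 5%, 10% and 20%. The probability of stopping for toxicity alone, at the stated boundaries, is:

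| Unexposed (assumed) | AZA group, N = 50 | LDAC arm, N = 26 |
|---|---|---|
| 0% | 0.676 | 0.488 |
| 5% | 0.580 | 0.414 |
| 10% | 0.478 | 0.342 |
| 20% | 0.285 | 0.215 |

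**The case against.** The strongest reply is that the plan never describes a patient continuing on AZA or LDAC alone after a failed Day 5 check. The check is placed among the exclusion criteria, so removal followed by replacement is a natural reading. Section 5.2.2.1 defines each arm as a combination, and 5.2.6 defines a cycle as including quizartinib. The DLT rules count patients treated at a dose level, and dose level 1 includes AC220, so an unexposed patient has arguably not been treated at that level. These patients also passed a screening QTcF limit and electrolyte criteria, so they may be few.

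This shows that the plan can be read safely, but not that it has to be: 4.2.8.1 says nothing about status, 5.3 does not list the failed check, and the only stated toxicity-evaluability rule is the one in 5.3.2.

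Several stronger readings are tempting, and the documents do not support them:
- **Everyone lost before Day 5 fills a phase I slot.** Section 5.2.5.4 already replaces non-toxicity losses before day 28 who had no DLT.
- **Phase II has no replacement rule.** Section 5.2.5.4 is not expressly limited to phase I. Whether it applies in phase II is unclear.
- **Unexposed patients are necessarily zeros.** The hematologic DLT definition has no AC220-attribution clause, so a patient on AZA or LDAC alone could meet it.
- **Section 5.3.2 is expressly the DLT denominator.** Neither 5.2.5 nor 12.2-12.3 refers to it. The link is the natural reading, not a stated one.

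**Conclusion.** The concern stands in a limited form. No section requires AC220 exposure for DLT counting, and two kinds of unexposed patient escape the replacement rule: those who stay on study on AZA or LDAC alone, and those removed for a non-DLT toxicity before any AC220. A single such patient among six moves the phase I rule noticeably, from 0.64 to 0.53 at a true rate of 0.33.

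These sizes are conditional illustrations, not forecasts. They rest on assumed unexposed counts, assumed true DLT rates and zero DLTs in the unexposed. If every failed Day 5 check in practice led to a non-toxicity removal, that route would cause no dilution wherever 5.2.5.4 is applied. The point merits correction because the outcome now depends on how a site reads an unstated status, and the correction is cheap.

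**What to change.** 1. In 5.2.5.4, 5.3.2 and 12.2-12.3, define the DLT-evaluable and toxicity-monitoring denominator as patients who received at least one dose of AC220.
2. In phase I, replace every patient who received no AC220 and had no DLT, whether or not the patient stays on study. State whether 5.2.5.4 applies in phase II.
3. Report any DLT-type event in an unexposed patient separately and have it reviewed, so that the exposure-based set does not silently drop it.
4. Keep the set of patients with a dose of either drug for adverse-event tables.
5. Reconcile 4.2.8.1 with 5.2.5.4 and 5.3, so that the study status of a patient who fails the Day 5 QTcF check is stated once. Which status applies is a clinical decision for the investigators.

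The cost is a few sentences and possibly one or two phase I replacements. The stopping boundaries do not change.
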